**Intervention Groups and Study Duration:**

The study will include a total of 8 visits and will be 17 to 20 weeks in duration (Figure 1-1): a 2-to 4-week Screening Period, a 2- to 3-week Preintervention Period, followed by a 12-week double-blind Study Intervention Period and 1-week Postintervention Period (Figure 1-1).

Participants that complete LIN-MD-64 have the option to enroll into the open-label, long-term safety study, LIN-MD-66, if they meet the eligibility criteria. Participants will be considered to have completed LIN-MD-64 if he/she has completed 12 weeks of double-blind study intervention, the end of treatment (EOT) visit (Visit 7), and the end of study (EOS) visit (Visit 8). However, the EOS visit in LIN-MD-64 is not required for participants who enroll into the open-label, long-term safety study LIN-MD-66 prior to that visit.

Participants will be randomized in a 1:1 ratio for 12 weeks during the double-blind study intervention period.

[figure not shown]
- FC participants receive either linaclotide 72 µg or placebo
- IBS-C participants receive either linaclotide 145 µg or 290 µg

Participants will be instructed to take their assigned dose orally as a single daily dose 30 minutes prior to any meal at approximately the same time each day, with the exception of the first dose at Day 1 (Randomization Visit) when participants will receive linaclotide or placebo in the clinic.

**Data Monitoring Committee:** Yes

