- a Study procedures for screening in LIN-MD-66 can be combined with End of Treatment (EOT)/Week 12 Visit (Visit 7) for Study LIN-MD-64.
- b Participants who rollover to the long-term safety study, LIN-MD-66, before the EOS Visit (Visit 8) are not required to have this visit.
- c Participants must complete at least 12 weeks (84 days) of study intervention before arriving at the study site for the EOT/Week 12 Visit (Visit 7). All randomized participants who prematurely discontinue from the study intervention, regardless of cause, should complete assessments at this EOT/Week 12 Visit (Visit 7).
- d The parent/guardian/legally authorized representative must provide written informed consent and the participant must provide assent before the participant's enrollment in the study. If a parent or legal guardian is also the participant's caregiver, he or she will be asked to sign a combined parent and caregiver written informed consent. Caregivers other than parent or legal guardian must provide written informed consent.
- e Prior to dosing, the investigator or appropriate site staff member will assess if Rome IV criteria for Child/Adolescent FC (FC and IBS-C participants) or Rome IV criteria for Child/Adolescent IBS (IBS-C participants) was met and record the outcome in the eCRF. Eligibility for the study is not based on this assessment.
- f Eligibility report must be run prior to randomization.
- g During the Screening Period, participants and their caregivers will receive information regarding lifestyle modifications (refer to Section 5.3 for details). There should be at least a 2-week interval between discussing the lifestyle modifications during the Screening Period and the participant's entry into the Preintervention Period.
- h Physical examinations will be performed by medically qualified site personnel and may be repeated at the investigator's discretion. If fecal impaction (as defined in footnote i) is documented during an optional repeat physical examination, the Study Physician must be notified.
- i Fecal impaction is defined as a hard mass in the lower abdomen identified on physical examination or a dilated rectum filled with a large amount of stool on rectal examination. If a rectal examination is performed, the medically qualified site personnel should assess for and document the presence of anal wink and normal anal tone.

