#### **9.1.5.2.1. Adverse Events**

An AE will be considered a TEAE if:

- The AE began on or after the date of the first dose of study intervention; or
- The AE was present before the date of the first dose of study intervention, but increased in severity or became serious on or after the date of the first dose of study intervention

An AE that occurs more than 1 day after the last dose of study intervention will not be counted as a TEAE

An AE will be considered a treatment-emergent SAE if it is a TEAE that additionally meets any SAE criteria.

The number and percentage of participants reporting TEAEs in each study intervention group will be tabulated by SOC and preferred term and by SOC, preferred term, and severity.

The number and percentage of participants reporting treatment-related TEAEs in each study intervention group will be tabulated by system organ class and preferred term.

If more than 1 AE is coded to the same preferred term for the same participant, the participant will be counted only once for that preferred term using the most severe and most related occurrence for the summarizations by severity and by causal relationship to study intervention.

Summary tables will be provided for participants with SAEs, AESIs, and participants with AEs leading to discontinuation if 5 or more participants reported such events. Listings of all AEs, SAEs, AESIs, and AEs leading to discontinuation by participant will be presented.

The definitions of an AE and SAE can be found in Section 10.3.

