### 10.3. Appendix 3: Adverse Events: Definitions and Procedures for Recording, Evaluating, Follow-up, and Reporting

#### 10.3.1. Definition of AE

AE Definition

 
An AE is any untoward medical occurrence in a participant or clinical study participant, temporally associated with the use of study intervention, whether or not considered related to the study intervention.
 
An AE can therefore be any unfavorable and unintended sign (including an abnormal laboratory finding), symptom, or disease (new or exacerbated) temporally associated with the use of study intervention.
 
 
For the purpose of the site’s data collection responsibilities, any untoward event that was reported from the time written consent was obtained until 30 days after the last known dose of study intervention is to be considered an AE. Particular attention must be given to the AE of diarrhea, which was the most frequently reported AE in the adult linaclotide program. Details about AE reporting are provided below.
 
Examples of AEs are as follows:
 
 
Changes in the general condition of the participant
 
Subjective symptoms offered by or elicited from the participant
 
Objective signs observed by the investigator or other study site personnel
 
All diseases that occur after signing the informed consent, including any change in severity or frequency of preexisting disease
 
All clinically relevant abnormalities in laboratory values or clinically relevant physical findings that occur during the study schedule
 
 
Please note medical procedures scheduled prior to consenting, but occurring during the study, should not be captured as AEs, but should be listed in the medical history if related to a pre-existing condition.
 
AE of Special Interest (AESI)
 
An AESI (serious or nonserious) is one of scientific and medical concern specific to the sponsor’s study drug or program, which warrants ongoing monitoring and rapid communication by the investigator to the sponsor. Such an event might warrant further investigation in order to characterize and understand it.
 
The following AESI(s) have been identified for the study intervention(s) in this protocol: significant volume depletion and/or significant electrolyte abnormalities and/or ECG abnormalities that are considered by the investigator or sponsor to be related to diarrhea. The investigator should contact the Study Physician if there is any question whether the criterion for an AESIs has been met.
 
All serious AESIs must be reported to the sponsor on an SAE form within 24 hours as noted below for SAEs.
 
Non-serious AESI do not require submission on an SAE form; rather, these events only need to be entered into the eCRF.

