#### 10.10.7. Week 12/End-of-Treatment Visit (Visit 7)

The participant must complete at least 12 weeks of study intervention before arriving at the study site for the Week 12 Visit. All randomized participants who prematurely discontinue from study intervention, regardless of cause, should complete assessments at this visit.

During the End of Treatment Visit (Visit 7), the following procedures will be performed:

- IWRS verification
- Perform a physical examination, including: general appearance, skin, HEENT (head, ears, eyes, nose, and throat), neck, thorax/lungs, cardiovascular, abdomen, musculoskeletal, lymph nodes, neurologic (including mental status), and visual inspection of the lumbosacral and perianal region. Breast and genitourinary examinations are optional at the discretion of the investigator.
- Complete Rome III assessment.

- Obtain height, weight, temperature (oral, rectal, or tympanic) and respiratory rate; and postural vital signs (supine and standing systolic and diastolic BP and pulse rate)
- Obtain standard 12-lead ECG (supine)
- Obtain clinical laboratory tests consisting of clinical chemistry, hematology, and urinalysis. All laboratory tests requiring blood draws should be collected at the same time
- Obtain urine pregnancy test for female participants of childbearing potential
- Review any AEs occurring since the last visit
- Review eDiary completion
- Review concomitant medications
- Review use of protocol-permitted rescue medication dispensed in IWRS where applicable. Participants may choose a different protocol-permitted rescue medication at any visit where available. Additional protocol-permitted rescue medications may be dispensed as needed at any visit
- Review study intervention and protocol-permitted rescue medications use and accountability.
- Study intervention will be returned
- For participants who enroll into LIN-MD-66 before the EOS Visit:
  - rescue medication will be returned
  - eDiary device will be returned

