6.4 SAFETY POPULATION

The Safety Population will consist of all participants in the Randomized Population who receive at least 1 dose of double-blind study intervention.

Participants will be summarized according to the study intervention they actually received for all safety analysis variables/endpoints. If a participant received study intervention other than randomized study intervention, actual study intervention received will be determined based on the study intervention received for the majority of the double-blind Study Intervention Period. If there is a tie, the higher dose will be considered the actual study intervention for that participant. The actual study intervention will be listed for the participants in the listing related to study intervention dosing information.

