11.1 ADVERSE EVENTS

Adverse events will be coded by system organ class and preferred term using the *Medical Dictionary for Regulatory Activities*, version 23.0 or newer.

An AE will be considered a treatment-emergent adverse event (TEAE) if

- The AE began on or after the date of the first dose of study intervention; or
- The AE was present before the date of the first dose of study intervention, but increased in severity or became serious on or after the date of the first dose of study intervention

An AE that occurs more than 30 days after the last dose of study intervention will not be counted as a TEAE.

An AE will be considered a treatment-emergent serious adverse event (TESAE) if it is a TEAE that additionally meets any SAE criterion.

The number and percentage of participants reporting TEAEs in each study intervention group will be tabulated by descending percentage in any group, by system organ class and preferred term, and further categorized by severity and causal relationship to the study intervention. If more than 1 AE is coded to the same preferred term for the same participant, the participant will be counted only once for that preferred term using the greatest severity and strictest causality for the summarization by severity and causal relationship. The above summaries of TEAEs, further categorized by severity and causal relationship will also be provided within each age group. If there are 5 or less participants with severe or related TEAEs in any study intervention group, the corresponding age group summaries for TEAEs by severity or causal relationship will not be provided.

The incidence of common ($\geq 5\%$ of participants in any study intervention group) TEAEs will be summarized by system organ class, preferred term, and study intervention group.

Summary tables will be provided for participants with TESAEs, AEs of special interest, and participants with TEAEs leading to premature discontinuation of study intervention.

For the Safety Population, separate listings will be presented for participants who died, participants with SAEs, participants with AEs leading to premature discontinuation, and participants with AEs of special interest. AEs during the Postintervention Period will also be included in the listings. Listing of all AEs will also be presented.

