17.0 CHANGES TO ANALYSES SPECIFIED IN PROTOCOL

There are no major changes to analyses specified in the amended protocol #1 (version dated June-2020).

The following other efficacy endpoint is added in Section 10.3 of the SAP.

- Change from baseline in participant-completed global severity items (pooping problems and tummy problems) at each week during Study Intervention Period

18.0 **HISTORY OF CHANGES**

Following changes have been made in this SAP Amendment:

- Section 6.3: Updated mITT population to include all participants in the Randomized Population who receive at least 1 dose of double-blind study intervention.
- Section 7.0: Removed the reasons for premature discontinuation from the study in participant disposition as there is no corresponding eCRF.
- Section 11.1: Modified TEAE definition to include any AE that occurs within 30 days (instead of 1 day) after the last dose of study intervention.
- Section 16.3.2: Modified the imputation rule for missing rescue medication (RM) use question. Missing RM usage will be considered as “used” for morning or evening diary if the other available assessment during that period indicated RM was taken.

19.0 **REFERENCES**

Ratitch B, and O’Kelly M. Implementation of Pattern-Mixture Models Using Standard

SAS/STAT Procedures. *In Proceedings of PharmaSUG 2011 (Pharmaceutical Industry SAS Users Group)*. Paper SP04. Nashville.

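### The 30-day TEAE window in both SAPs does not separate events that begin after the first open-label LIN-MD-66 dose, so in FC any such recorded event could count as a placebo TEAE

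*SAP*

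**What the plan says.** **TEAE limit.** Protocol section 9.1.5.2.1 states: "An AE that occurs more than 1 day after the last dose of study intervention will not be counted as a TEAE". Section 9.2.5.2 applies the same safety analyses to IBS-C. Section 11.1 of both SAPs states instead: "An AE that occurs more than 30 days after the last dose of study intervention will not be counted as a TEAE". The change is deliberate and recorded (FC SAP section 18.0, IBS-C SAP section 17): "Modified TEAE definition to include any AE that occurs within 30 days (instead of 1 day) after the last dose of study intervention".

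**Rollover.** The protocol synopsis says that Visit 8 is "not required for participants who enroll into the open-label, long-term safety study LIN-MD-66 prior to that visit". Footnote a of the Schedule of Activities lets LIN-MD-66 screening procedures be combined with Visit 7. Protocol section 10.10.7 gives Visit 7 return instructions "For participants who enroll into LIN-MD-66 before the EOS Visit".

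**AE collection.** Protocol section 10.3.1 treats as an AE "any untoward event that was reported from the time written consent was obtained until 30 days after the last known dose of study intervention". Section 8.3.2 collects AEs over the same period, at the scheduled timepoints and when observed or volunteered. It adds that investigators have no duty to seek AEs actively after participation ends.

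**Attribution.** Under FC SAP section 6.4, if a participant received something other than the randomized intervention, the "actual study intervention received will be determined based on the study intervention received for the majority of the double-blind Study Intervention Period". The safety arm is therefore always defined by double-blind treatment.

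**The concern.** Under the protocol's one-day limit, open-label treatment could barely enter the TEAE count. With 30 days it can, and neither SAP ends or splits the count when LIN-MD-66 dosing begins. A former FC placebo participant whose AE starts on open-label treatment, and is recorded in LIN-MD-64, would be tabulated as having a TEAE on placebo.

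The FC part is the trial's only placebo-controlled safety comparison. Events of this kind would raise placebo incidence for reasons unrelated to placebo, and a reader of the incidence table could not tell which events began after rollover. In IBS-C the consequence is smaller: an open-label event would be credited to a linaclotide dose group, with no placebo arm and no between-dose test.

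**Working it through.** The plan states no figure for this overlap, so there is none to reproduce. The check sets the rules side by side and counts days.

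**1. Where each FC safety summary stops (FC SAP)**
- Laboratory and ECG PCS counts (11.2, 11.4): double-blind intervention period.
- Vital-sign PCS counts (11.3): double-blind and postintervention periods tabulated separately.
- TEAEs (11.1): last dose + 30 days, with no split.
- Potential Hy's law (11.5.1): last dose + 30 days, with no split.

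The SAP adapts study completion (7.0) and visit windows (16.1, 16.2) for rollover participants, but not the TEAE rule.

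**2. Window length**

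Assume daily dosing on Days 1 to 84.
- Protocol: window ends on Day 84 + 1 = 85.
- SAPs: window ends on Day 84 + 30 = 114.
- Added: 114 − 85 = 29 days.

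**3. Possible open-label time inside the window**

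Let L be the last LIN-MD-64 dose day, S the first LIN-MD-66 dose day and w the limit in days. Overlap = max(0, L + w − S + 1). Take L as the day before Visit 7, which is also what FC SAP 16.5 imputes when the last dose date is missing. Table 1–1 places Visit 8 at 7 to 14 days after Visit 7. The documents do not give S, so these are scenarios:

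| First LIN-MD-66 dose | S | w = 30 | w = 1 |
|---|---|---|---|
| Visit 7 | L + 1 | 30 days | 1 day |
| Visit 7 + 7 | L + 8 | 23 days | 0 days |
| Visit 7 + 14 | L + 15 | 16 days | 0 days |
| After L + 30 | > L + 30 | 0 days | 0 days |

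**4. Effect per affected participant**

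Consider a placebo participant whose only event of a given term is a recorded open-label AE, with all 163 planned placebo participants dosed.
- One participant: 1/163 = 0.61 percentage points.
- At 189 per arm (only if the optional interim analysis is done): 1/189 = 0.53 points.

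The documents give no count of such participants. Assumed counts of 0, 1, 5 and 9 give 0, 0.6, 3.1 and 5.5 points. These show scale only and are not a forecast.

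**5. Can such an event be recorded?**

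Scheduled collection makes it unlikely: the last AE timepoint is Visit 8, which early rollovers may skip. The open route is an event that the site observes or the family volunteers within 30 days of the last dose, which sections 8.3.2 and 10.3.1 cover without a rollover exception.

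**The case against.** The strongest objection is that the harm depends on a step the documents do not show: an AE arising on open-label treatment being entered in the LIN-MD-64 database. Early rollovers skip Visit 8, return the eDiary at Visit 7, and count as completers then (FC SAP 7.0). Sites need not look for events afterwards. The LIN-MD-66 treatment, first-dose day, rollover share and AE data flow are not given. Combining screening procedures with Visit 7 does not mean that dosing starts there, so the 30-day overlap is a worst case. All of this stands, and it makes the frequency unknown and possibly nil. It does not close the gap, because spontaneous reports remain collectable to 30 days and the rule would then place them under placebo.

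Partial safeguards also exist. All AEs are listed, AE summaries are descriptive, and table specifications sit in a separate document that might contain a cut-off. Listings do not correct an incidence table, however, and the TEAE definition belongs in the SAP.

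A reader might infer two stronger claims. One is that the move to 30 days is itself an error. It is not: it matches the protocol's AE collection period and is openly documented. The other is that the placebo rate will be inflated and the linaclotide–placebo difference will shrink. The documents do not support this, because no count of recorded events is available and rollovers from the linaclotide arm could add events too.

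Finally, stopping the count on the day before the first LIN-MD-66 dose would, if that dose falls on L + 1, drop a day that the protocol counts. Any truncation also makes follow-up depend on rollover, which may relate to tolerability or response. Both points stand and shape the fix.

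**Conclusion.** The concern holds in a limited form. The SAPs' rule, applied as written, assigns any recorded post-rollover event within 30 days of the last dose to the double-blind arm, which in FC can be placebo. The possible open-label share of the window is 0 to 30 days, depending on an unstated first-dose date. Each affected placebo participant adds 0.61 points to a term's incidence, assuming 163 dosed placebo participants and no other event of that term in the participant. How many would be affected is unknown and may be none, and no change in the treatment difference can be estimated. This is a cheap improvement of low priority, mainly for FC, and not a demonstrated bias.

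**What to change.** In section 11.1 of both SAPs:
- Keep the 30-day limit, but exclude from the double-blind-arm TEAE tables any AE with onset after the day of the first LIN-MD-66 dose. List those AEs separately by former arm.
- Keep and flag AEs with onset on the day of the first LIN-MD-66 dose, so that the protocol's last dose + 1 day is preserved.
- Show post-dose follow-up time by arm.
- Give the TEAE table with the full 30-day window as a sensitivity display, because follow-up length will depend on rollover.

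In section 11.5.1 of both SAPs, flag, without excluding, any potential Hy's law case arising after the first LIN-MD-66 dose.

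The cost is a short addition to each SAP, one extra table and list, and a merge of the LIN-MD-66 first-dose date, whose availability at LIN-MD-64 database lock should be confirmed. The downside is shorter and unequal post-dose follow-up for rollover participants, so a delayed effect of double-blind treatment may appear only in the separate list and the sensitivity table. No participant procedures change. If no such event is recorded, no TEAE count changes.
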